5.1.4 Vaccine Distribution Procedures

Based on prior annual influenza vaccine use, we anticipate that KPNC will administer influenza vaccines to approximately 800,000 individuals aged 18–64 years, including 350,000 persons aged 50–64 years each season.

Approximately 400,000 doses of Flublok Quadrivalent vaccine and 400,000 doses of comparator SD-IIV will be administered to adults aged 18–64 years in each of the influenza seasons 2018–2019, 2019–2020, and 2020–2021.

There are approximately 70 facilities that receive individual influenza vaccine shipments from the KPNC Central Pharmacy (the exact number varies slightly each year; see **Figure 2** for an example of the flow). KPNC Central Pharmacy begins “autoshipments” to the Medical Centers and their satellite facilities’ main pharmacies in August in preparation for annual influenza vaccination clinics. For purposes of this study, medical center facilities include all associated satellite sites. KPNC Central Pharmacy determines the amount of vaccines to be shipped each day to the medical center facilities based upon vaccine use the previous year at each facility. For example, since Oakland Medical Center administered ~5% of all vaccines during the 2017–2018 influenza season, they would receive 5% of the daily shipment of vaccines during the subsequent 2018–2019 influenza season. Facilities may also request additional vaccine as needed.

Figure 2. Influenza Vaccine Distribution Flowchart Example

Once the facilities receive adequate influenza vaccines to distribute to all of their influenza vaccination clinics, they will prepare vaccine allotments for specific patient populations within each clinic (e.g., adult medicine, OB/GYN). We propose to randomize these facilities to distribute (and therefore administer) either Flublok Quadrivalent vaccine or a SD-IIV initially to all of their influenza vaccination clinics. Roughly half the facilities will first distribute Flublok Quadrivalent vaccine to be administered by their associated departments and clinics, while the other half will first distribute a SD-IIV for administration by their associated departments and clinics. The facilities will follow a weekly alternating schedule (with some variation due to usage) that indicates which vaccine is to be internally distributed to associated departments and clinics for the entire influenza season. Historically, >75% of vaccinations to adults aged 18–64 are administered prior to Thanksgiving.

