Because the study design specifies that roughly equivalent amounts of Flublok Quadrivalent vaccine and SD-IIV will be administered at every KPNC facility throughout the influenza season, KPVSC will monitor on a weekly basis that Flublok Quadrivalent vaccine and SD-IIV are being distributed as much as possible in a balanced way (see Section 11.1 for further details).

In order to randomize which facilities will initially administer Flublok Quadrivalent vaccine and which will start with a SD-IIV, we will block facilities by size and service area. For example, there may be 4 facilities per block, and within the block, 2 facilities start with Flublok Quadrivalent vaccine and 2 facilities start with a SD-IIV.

Staff Training: Pharmacy Staff, Influenza Clinic Injection Nurses, and Nurse Managers

KPVSC will work closely with the KPNC Central Pharmacy, the KPNC influenza program manager, the pharmacy staff, and influenza coordinators at the ~70 facilities to ensure that staff are aware of the study and are trained to carry out the study protocol. Randomization will be controlled by KPVSC, and the individual pharmacies will then distribute the vaccine to the departments and clinics based on the schedule determined by KPVSC. We will conduct trainings with the pharmacy staff, influenza coordinators, and department managers so that all relevant staff are aware that Flublok Quadrivalent vaccine or a SD-IIV should be routinely administered to everyone 18–64 years of age without any preference for one vaccine over the other, and that vaccine use should be based only on what is available in the clinic at the time of vaccination.

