In particular, we will emphasize that the injection nurse administering the vaccine should not preferentially choose one vaccine over the other, but instead use what is available in the refrigerator or portable cold storage box for the day. Based on routine influenza clinic operations, there is little potential for bias at the level of vaccine administration level (e.g., an injection nurse preferentially choosing one vaccine over the other), especially early in the season, when large numbers of influenza vaccine are administered on any given day; injection nurses are unlikely to spend time searching for a specific formulation based on preference. Further, by following the alternating vaccine supply schedule, we will reduce the likelihood that both Flublok Quadrivalent vaccine and SD-IIV are simultaneously available in the clinic. By having only one vaccine available for adults aged 18–64 years (Flublok Quadrivalent vaccine or SD-IIV), we hope to reduce the likelihood that an injection nurse is able to choose one vaccine over the other.

Because influenza vaccine is used at a very rapid pace once influenza clinics officially begin administering vaccine, the departments and clinics may request vaccine replenishment prior to the next distribution in order to ensure adequate supply. For this reason, it may be possible that a particular clinic will have both Flublok Quadrivalent vaccine and a SD-IIV available.

On a weekly basis, we will also monitor both the distribution of vaccine from KPNC Central Pharmacy to the facility pharmacies, as well as influenza vaccine administration. If we detect imbalances at either of these points, we will work closely with the affected facility(s) to attempt to correct the imbalance. Additional details may be found in Section 11.1.

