6.5 Randomization and Allocation Procedures

Subjects will not be individually randomized. A modified-cluster randomization scheme by facility will be deployed.

This study will employ a design whereby KPVSC will ensure that all clinics in KPNC will receive alternating distribution of Flublok Quadrivalent vaccine or SD-IIV. All KPNC facilities will follow a schedule that alternates which vaccine is supplied to each influenza clinic throughout the 3-year season period.

We will block facilities and randomize within blocks (see **Section 5.1.4**), ensuring that roughly half the facilities within each block initially administer Flublok Quadrivalent vaccine and the other half administer a SD-IIV. After the initial supply, the half that started with Flublok Quadrivalent vaccine will be supplied with the SD-IIV, and the half that started with SD-IIV will be supplied with Flublok Quadrivalent vaccine (see **Figure 1**). The supply of each clinic will then alternate between the two vaccines; that is, Flublok Quadrivalent vaccine alternating with SD-IIV with each delivery of vaccine to the clinics.

Figure 1: Visual of block randomization influenza vaccine administration schedule			
	Week 1	Week 2	Week 3
Block A			
Facility 1			
Facility 3			
Facility 5	Flublok	Comparator IIV	Flublok
Facility 7			
Facility 9			
Block B			
Facility 2			
Facility 4			
Facility 6	Comparator IIV	Flublok	Comparator IIV
Facility 8			
Facility 10			

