3.1 Study Design

To estimate the rVE of Flublok Quadrivalent vaccine versus SD-IIV against all PCR-confirmed influenza in vaccinees aged 18–64 years, this study will compare the incidence of PCR-confirmed influenza among Flublok Quadrivalent vaccinees versus SD-IIV vaccinees. Our primary comparison will be focused on adults aged 50–64 years at KPNC during the 2018–2019, 2019–2020, and 2020–2021 influenza seasons. We will also assess all adults aged 18–64 years for both influenza seasons.

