4.1 Primary Endpoints and Assessment Methods

Among all adults 50–64 years who receive either Flublok Quadrivalent or SD-IIV during the 2018–2019, 2019–2020, and/or 2020–2021 influenza seasons, we will estimate the relative vaccine effectiveness (rVE) of Flublok Quadrivalent vaccine versus SD-IIV against all PCR-confirmed influenza.

All microbiological testing is conducted at KPNC laboratories that have used real-time PCR tests for influenza since 2006. PCR results are categorized as positive for influenza A; positive for influenza B; or negative for both (PCR results are also categorized as

positive or negative for respiratory syncytial virus [RSV]). In the KPNC system, influenza PCR tests are used for clinical purposes, thus the "trigger" for an influenza PCR test is based on clinical presentation. The decision to test is up to each physician. KPNC monitors the influenza season which can affect the total amount of influenza testing in adults. Once the KPNC laboratories complete the PCR testing, the test result is updated in the patient's EMR.

Among adults aged 50–64 years who are vaccinated with Flublok or an SD-IIV, we plan to assess the number of adults who have a PCR-positive test ≥ 14 days after vaccination up through to the end of each influenza season (as determined by KPNC, which is generally when the proportion of influenza-positive PCR tests drops below 10%) or the first week of May, whichever is later, compared with those who do not have a PCR-positive test by vaccine received. To be included in the cohort for analysis, the PCR test must occur during the influenza season. The influenza season is defined as the first day that KPNC begins use of the Cepheid GeneXpert PCR assay for the influenza season (generally the first Tuesday of October); the end of the season is generally determined when the proportion of influenza-positive PCR tests drops below 10%, or the first week of May, whichever is later.

We will only count the first PCR positive test per patient in any single season.

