We do not know whether prior vaccination (i.e., booster or priming effect) affects VE of either Flublok Quadrivalent vaccine or SD-IIV, but we hypothesize that prior vaccination might be an effect modifier but not a potential confounder because what patients are vaccinated with in prior years should not be associated with what type of vaccine they receive in either of the 2 study seasons. We will test to ascertain if, as expected, there is (1) no correlation between prior vaccination (before the study period) and type of vaccination during the 3 study seasons, and (2) no correlation between the type of vaccine received in the one season and the type of vaccine received in the another study season. If we find that there is a relationship in any of these scenarios, we can treat prior vaccination (“prior” meaning before the study commenced, or “prior” as in vaccination in the first study season relative to the second study season) as a potential confounder. We would add variables that adjust for whether a patient was vaccinated during the past year(s), as well as which vaccine type they received. Further, if prior vaccination does modify VE, we may have adequate power to assess whether there is a boosting effect given our large sample size.

There is little possibility of confounding that may occur between patients tested versus those who are not tested. While not everyone with suspected influenza will be tested, the randomization process in vaccine supply (Flublok Quadrivalent vaccine versus SD-IIV) should result in an equal distribution of those who are and are not tested between the two vaccine groups throughout the season. We will attempt to mitigate possible bias and confounding as much as possible upfront by implementing our plans for supplying clinics with alternating shipments of vaccines. Because factors related to testing should be balanced, there is no reason to believe that the likelihood of being tested (conditional on influenza infection and severity) will be related to whether a person received Flublok Quadrivalent vaccine or SD-IIV. (It may be helpful to compare the RSV results of Flublok vs. SD-IIV vaccinees to assess our assumption of no residual confounding.)

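### The randomised facility schedule is never analysed: every comparison is by vaccine received, although departures from the schedule are foreseen and were to be accounted for

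*Protocol*

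**What the plan says.** **Allocation.** Protocol 6.5: "A modified-cluster randomization scheme by facility will be deployed". Facilities are blocked, the starting vaccine is randomised within blocks, and supply then alternates. Protocol 5.1.4 says that "the individual pharmacies will then distribute the vaccine to the departments and clinics based on the schedule determined by KPVSC", so a scheduled vaccine exists for each facility and week.

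**Departures.** The same section allows slippage: "The facilities will follow a weekly alternating schedule (with some variation due to usage". Clinics may ask for stock before the next distribution, in which case "it may be possible that a particular clinic will have both Flublok Quadrivalent vaccine and a SD-IIV available". Of the vaccinator it says only that "we hope to reduce the likelihood that an injection nurse is able to choose one vaccine over the other".

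**Comparison.** SAP 3.1: "this study will compare the incidence of PCR-confirmed influenza among Flublok Quadrivalent vaccinees versus SD-IIV vaccinees". SAP 4.1 counts positive tests in the primary endpoint "compared with those who do not have a PCR-positive test by vaccine received". Neither document defines a scheduled-vaccine variable.

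**Reliance on the schedule.** On influenza testing, SAP 5.1.1.2 argues that "the randomization process in vaccine supply (Flublok Quadrivalent vaccine versus SD-IIV) should result in an equal distribution" of tested and untested people between the vaccine groups. Protocol 11.1 makes the same argument.

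**Non-compliance.** Protocol 6.6 undertakes to document departures from the planned doses so that the analyses can take them into account. No SAP analysis does this.

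**The concern.** Randomisation protects the comparison of facility-weeks scheduled for Flublok with facility-weeks scheduled for SD-IIV. That protection passes to a comparison by vaccine received only if departures from the schedule are unrelated to influenza risk and to the chance of being tested. Where both products are in one clinic and nothing is blinded (Protocol 6.4), this is an assumption and not a property of the design.

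The fitted model does not restore the randomised contrast. As SAP 5.1.1.2 is written, risk sets are stratified on calendar day of follow-up and adjustment is through a facility-specific propensity score for the vaccine received. Neither conditions on facility by week of vaccination.

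At stake is bias in the primary hazard ratio, towards or away from Flublok depending on who is steered. With about 520,000 people per arm, a bias of a few per cent also visibly raises the chance of a false rejection.

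**Working it through.** **1. The plan's own figure.** Protocol appendix, age 50–64, PCR-positive influenza: 519,699 per arm, comparator risk 0.00205, two-sided alpha 0.05. For RR 0.85 the expected events are 519,699 × 0.00205 × 1.85 = 1,971. Schoenfeld: √1,971/2 × |ln 0.85| − 1.96 = 3.61 − 1.96 = 1.65, power 0.95. The likelihood ratio test named in the appendix gives 0.950, 0.659 and 0.216 for rVE 15%, 10% and 5%. The stated values are 0.95, 0.66 and 0.22, so they reproduce and no figure is disputed.

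**2. Possible bias by vaccine received.** The documents give no departure rate, so the inputs are assumptions: a share d of Flublok doses goes by choice to people whose unmeasured risk is k = 1.5 times that of others.
- Everyone else in both groups shares one mean risk: factor = 1 + d(k − 1).
- Worst case, in which every steered person would otherwise have had SD-IIV and displaces someone of average risk: factor = [1 + d(k − 1)]/[1 − d(k − 1)].

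| d | Shared-risk factor | Worst-case factor | A true rHR of 0.85 reads |
|---|---|---|---|
| 5% | 1.025 | 1.025/0.975 = 1.051 | 0.87 (worst 0.89) |
| 10% | 1.050 | 1.050/0.950 = 1.105 | 0.89 (worst 0.94) |

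If 1.5-fold is measured against the average of all vaccinees instead, the shared-risk factors are 1.026 and 1.054.

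The direction can reverse. With no true difference, d = 10% and k = 0.5, the factor is 0.95: a spurious rVE of +5%, rejected with probability 0.22 instead of 0.05. With k = 1.5 the apparent rVE is −5% and the rejection probability 0.21. These are unadjusted figures.

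**3. A milder case on a recorded factor.** The appendix's chronic-disease group is 103,940/519,699 = 20% of vaccinees, with risk 0.00286. The rest then have (0.00205 − 0.2 × 0.00286)/0.8 = 0.00185, a ratio of 1.55. If 10% of that group's doses are discretionary and all are Flublok, 55% of the group receive Flublok. The apparent rVE under no difference is about −1.6% and rejection 0.065, before the propensity score removes the measured part.

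**4. What an analysis by schedule would cost.** Let c be the share in each scheduled group given the other vaccine (an assumption). Then pF = 0.00205[(1 − c)RR + c] and pS = 0.00205[(1 − c) + c·RR]. For RR 0.85 and c = 10%, pF/pS = 0.865/0.985 = 0.878. The same likelihood ratio formula gives:

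| c | rVE by schedule (true 15%) | Power | Smallest true rVE with 80% power |
|---|---|---|---|
| 0 | 15.0% | 0.95 | 11.8% |
| 5% | 13.6% | 0.90 | 13.0% |
| 10% | 12.2% | 0.82 | 14.6% |
| 20% | 9.3% | 0.58 | 19.2% |

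These powers ignore clustering by facility and week, so they are upper limits if clustering inflates the variance.

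**The case against.** The objective is effectiveness in vaccinees, and Protocol 11.1 says that no vaccine is assigned to any patient. Comparison by vaccine received is therefore a legitimate primary analysis. This stands.

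The plan also does much to limit selection. Staff are trained to use whatever is in stock, and Protocol 5.1.4 explains why it sees little room for bias in a busy clinic. Distribution and administration are monitored weekly and corrected. SAP 5.1.1.2 does not lean on randomisation alone: it expects residual imbalance, excludes inpatient vaccinees and single-vaccine facilities, and adjusts for a propensity score that includes comorbidity, vaccination history and utilisation. The sentence about equal distribution concerns testing, not every confounder. All this narrows the concern, but these measures act on recorded factors.

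A reader might infer that nothing planned could reveal steering. The documents do not support that. The SAP suggests comparing RSV results between vaccine groups, tests whether vaccine type is related to prior vaccination, and checks balance before analysis. What can be said is that the RSV check, the one most sensitive to unrecorded factors, is not a commitment.

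A reader might also infer that the trial targets effects of 10–15%, so that any steering would swamp them. No target is stated: the appendix runs from 5% to 30% and the worked example in Protocol 11.2 is 30%. Nor do the documents describe choice by patients; they discuss the injection nurse.

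Finally, the scheduled vaccine is not sharply defined. Alternation is weekly in Protocol 5.1.4 but by delivery in 5.1.3 and 6.5, usage is adjusted when imbalance is seen, and Flublok may run out. This is a fair objection, and the remedy has to settle it.

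**Conclusion.** The gap is real and moderate. The plan has a randomised schedule, foresees departures from it and undertakes to make them available to the analysis, but specifies no analysis that uses the schedule. Selective use linked to unmeasured risk could bias the primary rHR in either direction.

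The documents do not show that such bias will occur or that the as-received analysis is an error. The size cannot be judged without a departure rate. The factors of about 1.03–1.05, and the worst case of 1.05–1.11, rest on an assumed 5–10% of Flublok doses steered to people at 1.5-fold risk, and shrink to the extent that the propensity score captures that risk. The worst case should not be read as the expected bias.

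**What to change.** Keep the as-received Cox model as primary and add to the SAP:

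1. **One sensitivity analysis of the primary endpoint**, using the same model with exposure set to the vaccine on KPVSC's original randomised schedule for that facility in the week of vaccination. Use that schedule and not the one later adjusted for usage, because adjustments respond to what was given. Limit the analysis to weeks in which both vaccines were still being supplied, and state whether facilities that used only one vaccine stay in.
2. **A concordance table**: the share of doses matching the schedule, by facility and week. This alone would show whether the concern has substance.
3. **A definite RSV negative-control comparison** in place of the optional wording.

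The cost is SAP text, one further model and one table. Vaccination date is recorded (Protocol 6.3.2.3), facility is already a covariate, and KPVSC sets the schedule. The drawback is dilution and loss of power, as shown in the working. The result should be read beside the primary estimate and the concordance, not as a replacement or a second test of superiority.

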5.1.5 Planned Study Calendar

The following dates are approximate. The actual dates may differ if there are manufacturing delays that affect Flublok Quadrivalent vaccine or SD-IIV vaccine(s).

Planned study period (total): August 2018 to May 2022

Anticipated first study member influenza vaccination date: September 16, 2018

Planned vaccination periods: August 2018 to April 2019, August 2019 to April 2020, August 2020 to April 2021

Planned date of draft study report: February 2022

Planned date of final study report: May 2022

5.2 Study Population

5.2.1 Recruitment Procedures

Eligible adults aged 18–64 years will receive either Flublok Quadrivalent vaccine or a SD-IIV in the course of routine influenza vaccination during each of the two influenza seasons of the study period.

5.2.2 Informed Consent Procedures

Not applicable. Because the present study is a prospective study using EMR data that are collected as part of routine clinical care, no informed consent will be required.

5.2.3 Screening Criteria

There are no screening criteria other than the inclusion and exclusion criteria.

5.2.4 Inclusion Criteria

An individual must fulfill all of the following criteria to be eligible for the study:

- Between the ages of ≥ 18 and < 65 years at the time of influenza vaccination
- Receive either Flublok Quadrivalent vaccine or SD-IIV at a KPNC facility during the study period from August 2018 through April 2021

5.2.5 Exclusion Criteria

An individual fulfilling any of the following criteria is to be excluded from the study to the extent possible:

- Children < 18 years old
- Adults ≥ 65 years old

5.2.6 Medical History

Prior to receiving an influenza vaccination (either Flublok Quadrivalent vaccine or SD-IIV), patients will be screened using an influenza vaccination screening form as part of a routine pre-vaccination assessment.

5.2.7 Contraindications for Subsequent Vaccinations

Severe hypersensitivity or adverse reaction to a previous dose of Flublok Quadrivalent vaccine or a SD-IIV.

5.2.8 Classification of Subjects Who Discontinue the Study

As this is not a clinical trial, there is not the possibility that a patient discontinues the study prior to completion. There is the possibility, however, that a patient is no longer a KPNC member at some point in the follow-up period following vaccination. Membership will be taken into account at the analysis stage to ensure that patients have adequate follow-up times.

5.2.9 Follow-up of Discontinuations

Not applicable.

5.2.10 Follow-up and Reporting of Pregnancies

We will include KPNC members who receive Flublok Quadrivalent vaccine or SD-IIV vaccine(s) while aged 18–64 years. Follow-up for outcomes based on PCR-confirmed influenza will include only the first positive PCR test (for influenza) per influenza season, and only if it is ≥ 14 days after vaccination, and follow-up will continue either through April 30 of each influenza season or until exit from KPNC, whichever occurs earlier. In the KPNC system, influenza PCR tests are used for clinical purposes, thus the “trigger” for an influenza PCR test is based on clinical presentation. The decision to test is up to each physician. KPNC also monitors the influenza season, which can affect the total amount of influenza testing at any point in the season.

Pregnancy is not an exclusion criterion for this study. Patients who are ≥ 18 years old and pregnant at the time of vaccination will be included in the analysis. Pregnant patients will be followed in the same way they normally would for routine influenza vaccination.

As described in Section 10.1, in the event that KPVSC reviews individual patient charts within the EMR and there is written notation in the medical record indicating that a health care provider attributed a serious or unexpected adverse event to Flublok Quadrivalent vaccine, KPVSC will report the adverse event possibly related to Flublok Quadrivalent vaccine.

